## **4. DESIGN OF THE CLINICAL INVESTIGATION**

### **4.1. General**

This is a prospective, multi-center, single arm clinical investigation to assess the proportion of lumbar spinal stenosis surgical treatment plans that change when an objective measurement of spinal stability is included and applied following a simple treatment algorithm.

#### **4.1.1. Minimization of Bias**

This will be a single-arm clinical investigation where each investigator records a surgical plan (prior to having access to the SPSI™ results, and then approves or rejects changes to the treatment plan based on the results of the SPSI™ metrics. Medical Metrics will provide the SPSI™ report prior to having access to the investigator's initial treatment plan. If the investigator rejects any changes to the surgical plan that would be required by an algorithmic application of the SPSI™ results, the investigator will be required to record a justification for the rejection. Any bias against the SPSI™ results would be evidence in a systematic rejection of changes required by an algorithmic application of the SPSI™ results.

#### **4.1.2. Primary Endpoints**

The primary endpoint is the proportion of lumbar spinal stenosis treatment plans that change when SPSI™ results are used in establishing the surgical plan.

This endpoint was chosen for the current study, since the outcome is critical to the design of subsequent research to answer the more important question of whether use of preoperative SPSI™ to select the optimal surgical treatment can improve clinical outcomes for patients. If the SPSI™ metric rarely changes the surgical plan, it may not be worth further pursuit of the SPSI™ metric. Conversely, if the SPSI™ metric changes the plan in a significant proportion of cases, then that knowledge can be used to help design subsequent research.

#### **4.1.3. Secondary Endpoints**

The secondary endpoint is the comparison of clinical outcomes (as measured by Oswestry Disability Index (ODI) and Numeric Rating Scale (NRS) leg pain/leg pain) at 12 months and 24 months in lumbar stenosis patients where the surgical plan was in accordance with the SPSI™ metric compared to historical controls.

If the SPSI™ metrics change the surgical treatment plan in a significant proportion of cases, the next question is whether the changes that the SPSI™ metrics support can lead to improved clinical outcomes, reduced reoperation rates, reduced use of pain medications and other clinical benefits. Without first documenting that investigators will use the SPSI™ metrics to change the surgical treatment plan, a clinical study to determine if the SPSI™ metrics can improve outcomes was not justified. However, the results of the proposed study will provide data that can be analyzed for evidence to support the hypothesis that use of SPSI™ metrics can help to decide if fusion should be performed in addition to decompression of a stenotic lumbar level. That analysis will be valuable in the design of subsequent research.

#### **4.1.4. Exploratory Endpoints**

The following exploratory endpoints will be assessed:

- Does the presence of a facet fluid sign as indicated by the investigator on preoperative MRI correlate to instabilities specified by SPSI™ results?
- What is the rate of instability (defined as a  $> 1$  standard deviation increase in SPSI™) 12 months after decompression (no fusion) surgery, how do these rates compare to the published data (for example Guha et al [40] and Cushnie et al [41] ), and does the development of post-decompression instability have an effect on the change in ODI or NRS scores relative to preop?
- What are the reoperation rates at 12 months following decompression alone and following decompression plus fusion, and how do these rates compare to published data from studies where similar inclusion and exclusion criteria were used and patients were randomized to decompression alone or decompression plus fusion [3, 42]?
- Does a nonunion following decompression plus fusion surgery have an effect on the change in ODI or NRS scores relative to preop ?

#### **4.1.5. Safety Endpoint**

The safety endpoint will be the nature and frequency of all adverse events observed during the clinical investigation including their timing, severity and relatedness to the investigational device and/or clinical investigation procedures.

#### **4.1.6. Equipment for Assessment**

High-quality flexion and extension radiographs are required for all subjects, both preoperatively and at 12 months follow-up. High-quality is defined as visualizing all levels from L1 to S1 and having at least 5 degrees of intervertebral rotation between flexion and extension, and the ability to clearly identify the four corners of each vertebra in both the flexion and extension radiographs. All radiographs must be provided in digital format, with images created by either a computer radiography or digital radiography system. Photographs of an x-ray on a view box are not acceptable. During site-screening, the x-ray equipment that will be used to collect the flexion-extension radiographs will be assessed for ability to provide the required quality. That includes the ability to easily position the x-ray source and detector to capture the spine in the fully flexed and fully extended positions, the ability to transmit x-rays to MMI in

digital format, as well as the ready availability of a walker required for patient support during image acquisition.

#### **4.1.7. Subject Replacement**

Subjects that are enrolled but who fail screening, or where the post-SPSI™ surgical plan is not in accordance with the SPSI™ metric (either because the investigator chooses not to follow the SPSI™ metric, or the SPSI™ for applicable level will be recorded as “NA”), or do not receive surgery, will be replaced.

### **4.2. Investigational Device and Comparators**

No comparator device will be used to address the endpoint s of this study.

### **4.3. Subjects**

#### **4.3.1. Inclusion Criteria**

- 1) Symptoms consistent with single level lumbar spinal stenosis based on judgment and experience of the investigator
- 2) Central and or foraminal stenosis confirmed by MRI as per the investigators clinical standards
- 3) Grades 1 (10 to 25%) or 2 (26 to 50%) anterior or retro-spondylolisthesis using the Meyerding scale [43]
- 4) Absence of lateral spondylolisthesis
- 5) No prior lumbar spinal surgery
- 6) Absence of American Society of Anesthesiologists (ASA) class IV or higher disease
- 7) The single level surgical technique planned (prior to viewing the spinal motion report) to decompress the level is not expected to destabilize the spine (fusion is not deemed necessary due to probable iatrogenic instability)
- 8) Prior to viewing the spinal motion report, the surgical plan includes decompression or decompression and fusion of only one level
- 9) Based on the investigators subjective assessment, the patient is able to flex and extend sufficiently to facilitate acceptable flexion and extension radiographs
- 10) The fusion technique planned prior to viewing the spinal motion report is the following:  
Instrumented posterior (pedicle screws and rods) with / without PLIF cage
- 11) Subject is able to understand and sign the study Informed Consent Form
- 12) Subjects is at least 18 years of age.
- 13) Subject has willingness and ability to comply with study procedures and visit schedules and able to follow oral and written instructions

#### **4.3.2. Exclusion Criteria**

- 9) Lumbar stenosis without spondylolisthesis
- 10) Severe lumbar stenosis that requires a wide decompression where the investigator believes (based on experience and available research studies) that the decompression will destabilize the spine and fusion surgery is required regardless of preoperative SPSI™

- 11) Pregnant women
- 12) Scoliosis involving a lumbar curve greater than 10 degrees
- 13) Stenosis at the level of a transitional vertebra
- 14) Lateral spondylolisthesis (Coronal plane translational misalignment between vertebrae)
- 15) Prior lumbar spinal surgery
- 16) American Society of Anesthesiologists (ASA) class IV or higher disease

#### **4.3.3. Subject Withdrawal, Discontinuation and Study End**

A subject may withdraw or discontinue its participation at any time during the clinical investigation. He/she does not have to give a reason for withdrawal. Subjects may also be withdrawn from the clinical investigation by the investigator for non-compliance with clinical investigation plan, due to adverse events or if the investigator feels it is in the subject's best interest to stop. Subjects withdrawn due to an adverse event will be followed until resolution of the adverse event or 30 days, whichever is the shorter time. Withdrawn subjects will be replaced in accordance with section 5.1.7, other withdrawn subjects will not be replaced. The reason for subjects' withdrawal or discontinuation will be recorded. Any data collected up until the time of withdrawal of the subject will be used for analysis. After study end, subjects will receive medical care according to standard of care, if applicable.

#### **4.3.4. Enrollment**

A subject is considered enrolled in the clinical investigation after they have provided written informed consent. A subject is considered treated per algorithm if the post- SPSI™ surgical plan is in accordance with the SPSI™ metric and if the subject has received surgery. A subject who is enrolled in the clinical investigation, but does not comply with the inclusion and exclusion criteria is considered a screen-failure.

#### **4.3.5. Total expected duration of the clinical investigation**

The clinical investigation is expected to take approximately up to 41 months including the enrollment period.

#### **4.3.6. Expected duration of subject's participation**

Time from the subject's consent for participation in the clinical investigation until surgery is up to 3 months. Each subject will be followed for two year after surgery. The total expected duration is therefore up to up to 27 months.

#### **4.3.7. Enrollment period**

The enrollment period is expected to take approximately 14 months.

#### **4.3.8. Number of Subjects**

A total of 65 "treated per algorithm subjects" will be included. A subject is considered "treated per algorithm" if the post- SPSI™ surgical plan is in accordance with the SPSI™ report and if the subject has received surgery. Each clinical site contributing to the clinical investigation is expected to enroll at least 20 subjects.

## 4.4. Procedures

### 4.4.1. Schedule of Assessments

TABLE 2. SCHEDULE OF ASSESSMENTS

Assessment	Visit 1 Screening (≤ 3m to surgery)	Pre-surgery phase	Visit 2 Surgery	Visit 3* 6m (±30d)	Visit 4 12m (±30d)	Visit 5 24m (±30d)
Informed Consent	X					
Demographics	X					
Medical History	X					
MRI	X #					
Flexion/Extension X-rays	X				X	
Surgical Plan – pre SPSI™ (P1)		X				
SPSI™ metric		X			X	
Surgical Plan – post SPSI™ (P2)		X				
Actual Surgery Performed (P3)			X			
Oswestry Disability Index	X			X	X	X
Numeric Rating Scale leg pain	X			X	X	X
Patient satisfaction				X	X	X
Collection of reoperation data					X	X
Collection of analgesic use data	X				X	X
Collection of Adverse Event data			X		X	X

# MRI done as part of standard of care.

\*This visit can be done over the phone.

### 4.4.2. Visit 1 - Screening (≤3m to surgery)

Consecutive lumbar stenosis patients that are planned to undergo lumbar decompression surgery or lumbar decompression plus fusion (based on symptoms, MRI-based confirmation of stenosis and severity of stenosis, and the investigator's current clinical decision making process), will be asked to participate in the clinical investigation. Subjects must have an MRI exam available (performed per standard of care) that was used to confirm stenosis, as well as images that were used to document spondylolisthesis per the investigator's standard of care. Prior to performing any activities/evaluations related to the clinical investigation, except the standard of care assessments, the subject must be thoroughly informed about all aspects of the study, including scheduled visits and activities, and must have signed the informed consent approved by the Ethics Committee. The screening visit may occur at any time within 3 months prior to surgery.

During the screening visit the following assessments will be performed:

#### 4.4.2.1. Informed Consent

Informed consent procedure will be performed as described in section 14.

#### **4.4.2.2. *Demographics***

Recording of patient baseline characteristics (e.e. age, gender, race, ethnicity) will be completed at screening.

#### **4.4.2.3. *Medical History***

Recording of the subject's relevant medical history (up to 5 years prior to screening) will be completed. Medical history is considered relevant when related to any of the study eligibility criteria, when it may influence the conduct of the study, or when it may affect any of the study endpoints, at the discretion of the investigator.

#### **4.4.2.4. *Standard of care MRI***

A standard of care MRI exam will be used to confirm stenosis. The MRI exam is considered standard-of-care in the management of spinal stenosis patients as it is the primary tool for verifying the presence and extent of stenosis. This MRI will also be used to determine the presence of facet fluid sign. The facet fluid sign is observation of an abnormally wide area of high signal intensity in the left and/or right facet joints. The observations will be done by the investigator.

#### **4.4.2.5. *Pre-surgery Flexion-Extension Radiographs***

Flexion-extension radiographs will be obtained following a study-specific radiographic protocol to help assure that all x-rays will be of high-quality. The subject will be asked to watch a training video available on YouTube prior to collection of the radiographs. The training video will help to assure that the subject is aware of what is required of them to obtain radiographs of high-quality. During image acquisition, the subject will be asked to stand in front of a standard walker. Using the walker for support, the subject will bend forward as instructed in the video, and the flexion radiograph will be obtained. The subject will then be asked to use the walker for support as they bend backwards, as instructed in the training video, and the extension radiograph will be obtained. The flexion and extension radiographs will be electronically sent to MMI for analysis. The site will be responsible for assigning a study-specific identification number to the subject, and for providing that study-specific number to MMI along with the flexion and extension radiographs.

#### **4.4.2.6. *Oswestry Disability Index***

The Oswestry Disability Index (ODI) version 2.1a is a validated patient reported outcome and is used to indicate the extent to which a person's functional level is restricted by disability. The ODI consist of ten topics concerning intensity of pain, lifting, ability to care for oneself, ability to walk, ability to sit, sexual function, ability to stand, social life, sleep quality, and ability to travel. Each topic has 6 potential answers consisting of statements related to the topics. The subject checks the statements which most closely resembles their situation. Each question is scored on a scale of 0–5 with the first statement indicating the least amount of disability (scored 0) and the last statement indicating most severe disability (scored 5). The scores for all questions answered are summed, then multiplied by two to obtain the index (range 0 to 100). Zero equates to no disability and 100 relates to the most severe disability. The ODI will be collected on paper after which it will be entered into the electronic case report form (eCRF).

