### 5.2. **Secondary Endpoint**

#### **Comparison of clinical outcomes in lumbar stenosis patients where surgical planning including SPSI™ compared to historical controls**

After 12 month ( $\pm$  30 days) the change from baseline (12 month minus PreOp) in both the ODI, and the region-specific NRS [46-48] leg pain score will be calculated for each subject in the study. These outcomes instruments have been used in many spine studies, are well-accepted, and there is reference data in the literature that can be used to help interpret results from the proposed study. The secondary endpoint analyses will be done using the per-algorithm population. The per-algorithm population includes all patients where the surgeon modified the initial surgical plan as needed per the algorithm defined in Table 1.

The purpose of the ODI is “To indicate the extent to which a person’s functional level is restricted by disability”. The mean and standard deviation for the 12 month ODI, and the change in the 12 month ODI relative to baseline in study subjects will be compared (using a T-test) to the mean and standard deviations expected from peer-reviewed publications that have randomized lumbar stenosis patients to either decompression only or decompression and fusion. Most of this literature is already available at MMDx but an updated search will be completed using Google Scholar and pubmed prior to the data analysis so that any recent literature can be included. The data analysis will be repeated after 24 month outcomes have been collected.

The comparison of study data to historical control data can be done for each historical control study that has comparable data. The expected rate will be based on a review of the available literature. Many peer-

---

 <https://eprovide.mapi-trust.org/instruments/oswestry-disability-index>

reviewed publications do not report means and standard deviations in a manner that allows for use of their data directly as a historical control [4] although the data can nevertheless help to support choice of numbers to use. Table 5 summarizes some of the studies that provide historical control data.

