Most of the prior literature reports a similar improvement in outcome scores for patients treated with decompression only versus decompression and fusion. The null hypothesis is that the use of SPSI™ report by investigators to select levels to treat and the type of surgery to use will NOT effect the improvement in clinical outcomes for lumbar stenosis patients treated with decompression only or decompression plus fusion. The null hypothesis would be rejected if, when SPSI™ is used to select treatment, the improvement in outcome scores is significantly better than reported in the peer-reviewed literature. Although it is unlikely that the sample size in the current study will be sufficient to address the null hypothesis with an acceptable significance level and statistical power, the data from this pilot study will be used to help establish sample sizes required to more definitively document the clinical benefit of SPSI™ for selecting levels and treatments in lumbar spinal stenosis patients.

TABLE 5: A SAMPLING OF PAPERS THAT PROVIDE POTENTIAL REFERENCE ODI AND NRS DATA. A MORE COMPLETE LIST WOULD BE GENERATED PRIOR TO INTERPRETING THE STUDY RESULTS BASED ON A COMPLETE LITERATURE REVIEW AND CONSULTATION WITH THE PARTICIPATING INVESTIGATORS TO ASSURE THAT THE HISTORICAL CONTROL DATA INCLUDE THOSE PUBLICATIONS THAT THE INVESTIGATOR USES TO INFORM PATIENTS ON EXPECTED OUTCOMES.

Study	FU Months	N	Delta ODI		Delta NRS Leg Pain	
			D	D&F	D	D&F
Weinstein 2010	24	109	-16.1(19.8)			
Austevoll	12	260/260	-17.5[16.1]	-19.7[18.3]	-3.0[2.9]	-3.5[2.8]
Ghogawala	12	35/31	-22.2[NR]	-26.1[NR]	NR	NR

Key to abbreviations in Table 5:

Delta ODI: The change in the Oswestry Disability Index at follow-up (FU) relative to PreOp.

Delta NRS Leg Pain: The change in the visual-analog score for patient reported leg pain.

D: Decompression surgery only

D&F: Decompression surgery and fusion surgery

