#### **5.3.2. Exploratory research question 2: Proportion of levels treated using decompression only that have an increase in SPSI™ at 12 months**

As previously noted, one common justification for adding fusion surgery to surgery for decompression of lumbar stenosis, is that the decompression may create an instability that will later need to be treated. The fusion surgery is sometimes used prophylactically against the possibility of developing instability following decompression surgery. However, if instability rarely develops, this justification is not appropriate. Multiple research studies have been published providing data on the low-proportion of patients that develop instability following decompression-only surgery [7, 40, 49-54]. However, it is somewhat difficult to fully accept those studies since there are also scientific reviews concluding that there is currently no validated method for diagnosing instability [13]. Therefore, the proportion of patients where SPSI™ increases significantly following decompression-only surgery will be determined using an objective metric for spinal stability. This analysis will be completed as simple descriptive statistics and also using a simple test of proportions in comparison to the proportion of patients reported in prior publications. There is some evidence that a high translation-per-degree-of rotation can be associated with low-back symptoms [19]. In addition, there is some evidence that increased spondylolisthesis following decompression may be associated with worse outcomes [55, 56], so a binary classification (significantly increased SPSI™ versus no change in SPSI™) will be analyzed as a covariate when analyzing clinical outcome scores. If the change in SPSI™ is greater than +0.75, then that patient will be classified as having increased SPSI™. Otherwise, the patient will be classified as having no significant change. This endpoint will be analyzed using the Per-algorithm Population.

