## **5.7. Missing Data**

No imputation or adjustments for missing data will be performed. All available data will be analyzed per the defined analysis populations.

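### The ODI scoring rule is correct only for complete forms; applied as worded to an incomplete form, it counts each skipped item as 0

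*Combined protocol and SAP*

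**What the plan says.** Section 4.4.2.6 describes ten topics, each scored 0 (least disability) to 5 (most severe), completed on paper and then entered in the eCRF. The scoring rule is: "The scores for all questions answered are summed, then multiplied by two to obtain the index (range 0 to 100". The follow-up visits (4.4.5 to 4.4.7) refer back to this description.

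Section 5.7 has two sentences on missing data: "No imputation or adjustments for missing data will be performed" and "All available data will be analyzed per the defined analysis populations". Neither mentions single items within a questionnaire.

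The ODI is used in three places:

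- Secondary endpoint (5.2): "The mean and standard deviation for the 12 month ODI, and the change in the 12 month ODI relative to baseline" are compared by t-test with published values, and "The data analysis will be repeated after 24 month outcomes have been collected". The null hypothesis is to be rejected if "the improvement in outcome scores is significantly better than reported in the peer-reviewed literature".
- Exploratory question 2 (5.3.2): a binary indicator of increased SPSI "will be analyzed as a covariate when analyzing clinical outcome scores".
- Exploratory question 4 (listed in 4.1.4): "Does a nonunion following decompression plus fusion surgery have an effect on the change in ODI or NRS scores relative to preop".

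**The concern.** The rule sums whatever was answered and then applies a fixed multiplier of two. That multiplier is right for ten answers only. With fewer answers the scale shortens, and a blank has the same effect as the best possible answer. A rule that in effect fills blanks with zeros sits badly with a section that rules out imputation.

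The secondary comparison has no concurrent arm. A scoring artefact in the study data is therefore not balanced by the same artefact in a control group scored by the same people, and the document does not say how the published studies scored incomplete forms. Section 5 also has the data analyzed both by the sponsor and by an independent statistician. Without an explicit rule, the two could score the same partial form differently, or the choice could be made after scores are known. Sections 3 and 5.2 intend these outcome data to inform later research, and 5.2 names its sample size, so the scores matter even though the comparison is not expected to be well powered.

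**Working it through.** **Inputs.** Ten items scored 0 to 5, rule 2 x sum of answered items, stated range 0 to 100 (4.4.2.6). ODI changes of -17.5 [16.1] for decompression and -19.7 [18.3] for decompression plus fusion, 260 patients per arm (Table 5). The key to Table 5 does not define the brackets; I read them as SDs. Target of 65 subjects, at least 59 analyzed (5.5). Skip rates and baseline ODI are not in the document and are assumed below.

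**1. The plan's own range.** 10 x 5 x 2 = 100, so the stated range reproduces for a complete form.

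**2. Incomplete forms.** With k items answered the maximum is k x 5 x 2 = 10k: 90 for nine, 80 for eight, 70 for seven. A blank adds nothing to the sum, so the result equals that of a ten-item form with blanks set to 0. The loss per skipped item is 2 x its true score, from 0 to 10 points.

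**3. Example, every answered item scored 3.**

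| Items answered | Rule as worded: 2 x sum | 100 x sum / (5 x items answered) |
|---|---|---|
| 10 | 60 | 60 |
| 9 | 54 | 60 |
| 8 | 48 | 60 |

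**4. Direction.** The ODI at any one visit can only be understated. The change score can move either way. Take a true change of -17.5, an assumed baseline of 40 or 50, and one skipped item of average score, so that the form keeps 0.9 of its value:

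| Item skipped at | Baseline 40, follow-up 22.5 | Baseline 50, follow-up 32.5 |
|---|---|---|
| Follow-up alone | 0.9 x 22.5 - 40 = -19.75 | 0.9 x 32.5 - 50 = -20.75 |
| Baseline alone | 22.5 - 0.9 x 40 = -13.5 | 32.5 - 0.9 x 50 = -12.5 |
| Both visits | 0.9 x (-17.5) = -15.75 | 0.9 x (-17.5) = -15.75 |

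A skip at follow-up alone inflates improvement; a skip at baseline alone hides it.

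**5. Group mean, illustration only.** If a share q of subjects skips one item of average score at one visit, the mean shifts by q x ODI/10. With q from 5% to 30% and a true ODI of 20 to 60, this runs from 0.05 x 2 = 0.1 to 0.30 x 6 = 1.8 points. If the same average item is skipped at both visits, the mean change shrinks by q x change/10: 0.05 x 1.75 = 0.09 to 0.30 x 1.97 = 0.59 points.

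These are not bounds, because the skipped item need not be average. If 30% of subjects skip an item truly scored 5, the mean shifts by 0.30 x 10 = 3.0 points; if the item is truly 0, it does not shift.

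**6. Scale.** The standard error of the difference between 65 study subjects and a 260-patient historical arm is

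- SD 16.1: sqrt(16.1²/65 + 16.1²/260) = 2.23
- SD 18.3: sqrt(18.3²/65 + 18.3²/260) = 2.54

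so about 2.2 to 2.5 points. With 59 subjects the same formula gives 2.3 to 2.6.

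**The case against.** The strongest reply is that the paragraph describes the complete instrument. Its range and its meaning for a score of 100 hold only when ten items are answered, and read that way it is right. Section 5.7 does not instruct anyone to score partial forms: its sentence against imputation supports leaving such a form without an index as readily as its sentence on available data supports scoring it. The plan names a validated, versioned instrument (2.1a), and a footnote in 5.2 points to its distributor's page. Any instructions there on skipped items cannot be checked from the document. The effect is probably small, the primary endpoint is untouched, and 5.2 itself says the sample is unlikely to be sufficient for the outcome hypothesis.

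Much of this stands. A reader might infer that the plan commits to scoring blanks as zero, or that 4.4.2.6 and 5.7 contradict each other. The document supports neither: 5.7 is silent on skipped items, so this is something that could happen, and the relation between the sections is a tension.

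What does not stand is that the text needs no change. The rule refers to questions answered, not to all ten. The form is filled in on paper, and no completeness check is described. If only complete forms are to be scored, the plan should say so.

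**Conclusion.** The rule as worded gives a wrong index for an incomplete form whenever a skipped item's true score is above 0, and nothing else in the document corrects it. That part is arithmetic and certain: each skipped item costs 0 to 10 points. Complete forms are scored correctly.

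The group effect is unknown, because no skip rate is given. On the assumed rates and an average skipped item it stays below the standard error of the comparison; an untypical item could take it above. Probably modest is a fair summary.

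A reader might also infer that the rule tilts the secondary comparison in favour of SPSI. That holds for the ODI level in the study data, which can only err towards less disability. It does not hold for the change score, on which the null hypothesis is judged and which can err either way. With the published studies' handling of partial forms also unknown, the net effect on the comparison has no known sign.

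The point is limited to the ODI secondary endpoint and the ODI parts of exploratory questions 2 and 4. The primary endpoint and the sample size are not affected. It should be corrected before any ODI data are analyzed.

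**What to change.** In 4.4.2.6, replace the scoring sentence with one rule for all forms: index = 100 x (sum of answered items) / (5 x number of items answered), with a prespecified minimum number of answered items, chosen by the sponsor, below which the score is missing. Because this is itself a way of handling skipped items, add one sentence to 5.7 saying that the scoring rule is not an imputation or adjustment barred by that section.

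An acceptable alternative, which fits 5.7 as written, is to state in 4.4.2.6 that any incomplete form is missing. Its price is lost subjects. If 5% to 30% of forms per visit are incomplete (assumed), the number of the 65 subjects with a change score would be

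- about 62 to 45 if the same subjects skip each time (65 x 0.95 = 61.8; 65 x 0.70 = 45.5)
- about 59 to 32 if skips are independent between visits (65 x 0.95² = 58.7; 65 x 0.70² = 31.9).

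Either way the cost is one replaced sentence, plus one added sentence under the first option. No visit or assessment is added, and complete forms score the same under both.
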